Use of Nitrous Oxide Donor for Labor Induction in Women with
PreEclampsia (NOPE)

NCT03171480

November 2017

**Use of Nitrous Oxide Donor for Labor Induction in Women with PreEclampsia or
Gestational Hypertension (NOPE): A Randomized Controlled Trial**

Draft Protocol

[name] MD
The Ohio State Wexner Medical Center
Department of OB/GYN, Maternal Fetal Medicine

November 2017

Version 1.2

1. Introduction

1.1 Background:

Hypertensive diseases of pregnancy, including preeclampsia and gestational hypertension affects at least 5-10% of all pregnancies. Preeclampsia is the most severe form and is a rapidly progressive condition characterized by high blood pressure and the presence of protein in the urine. Gestational hypertension is defined as systolic blood pressure (SBP) >140 mmHg and diastolic blood pressure (DBP) >90 mmHg and approximately half of women diagnosed with gestational hypertension will progress to preeclampsia.

To date there is no cure for preeclampsia except delivery. Given the potential of adverse consequences for both mother and fetus, preeclampsia and gestational hypertension is the leading diagnosis triggering medically indicated preterm birth. Therefore, most patients with gestational hypertension or preeclampsia who require delivery will not be in spontaneous labor and must undergo induction of labor. The obstetrician then faces a dilemma regarding the optimal method of induction. As to date there is no consensus to guide the physician on the best method for induction of labor. The ideal induction agent(s) should result in a relatively short induction to delivery interval without risk to fetus and with low rates of cesarean sections. The induction to delivery interval and low rates of CD is especially important in preeclampsia, to minimize significant maternal and infant morbidity associated with CD and to preventing worsening of disease.

Nitric oxide (NO) is a free radical that plays a fundamental role in human physiology, being involved in the homeostasis of different functions. In obstetrics, this molecule is determinant in the physiology of labor and cervical ripening and it has been implicated as playing a fundamental role in the etiology of preeclampsia. In blood vessels, NO is a potent vasodilator and platelet-aggregation-inhibitor. It has been postulated that lack of NO during gestation is related to the development of gestational hypertension and preeclampsia. Studies investigating the replenishment of NO in preeclampsia have shown improvements in blood pressure, uterine artery pulsatility index (which is classically abnormally high in preeclampsia), and a reduction in platelet activation.

Another proven role of NO, is induction of the physiological process of cervical ripening. Compelling animal data showed that all known Nitric-Oxide Synthase isoforms (iNOS, nNOS, eNOS) were present in the cervix. An increase in iNOS occurred during labor at term compared with early gestation. In rats, during preterm labor, iNOS concentrations increased significantly in the cervix. Labor duration was significantly prolonged when NOS was inhibited by L-NAME. Furthermore, cervical extensibility decreased significantly after in-vitro incubation with L-NAME. Overall, the above experimental data suggests NO system plays an active role in the cascade of processes involved in preparing the uterus and cervix for parturition, and its administration can speed the process of cervical dilatation.

Human cervical tissues display the same augmentation of iNOS, in women approaching term. NO-production in the cervix is low during gestation and becomes upregulated once pregnancy advances to term. Vaginal application of NO releasing drugs is effective on pre-induction cervical ripening process of the labor. It directly and through stimulation of prostaglandin and cyclooxygenase-2 (COX2), release of cytokines, and

inhabitation of thromboxane-A₂ (TXA₂) facilitates cervical ripening without causing complications such as fetal distress. Several clinical trials have ascertained the ability of the topical application of NO donors to promote cervical ripening, and labor induction.

Recent evidence has emerged about the role that locally applied NO donors play in cervical ripening and that NO-donors are effective and safe cervical ripening agents. A recent Cochrane Database review of the existing evidence in humans suggest that NO donors can be a useful tool in the process of induction of labor causing the cervix to be more favorable in comparison to placebo. The authors concluded that, additional data are needed to assess the true impact of NO donors on all important labor process and delivery outcomes.

We hypothesize that using a NO donor as an adjuvant to misoprostol/ intra-cervical Foley bulb for induction of labor in women with gestational hypertension and/or preeclampsia will have a synergistic effect by ripening the cervix, and shortening the overall duration of labor. If our hypothesis is confirmed, this approach may represent a significant advancement in clinical care because it will potentially significantly decrease the rate of Cesarean delivery women with gestational hypertension or preeclampsia, where the rates of surgical interventions are very high. The existing evidence also implies the NO adjuvant method will be reducing maternal blood pressures, thereby decreasing the utilization of intrapartum anti-hypertensives.

Here, we propose a randomized controlled trial (RCT) of nitric-oxide donor (NOD) isosorbide mononitrate (IMN) versus placebo as an adjuvant to misoprostol/ intra-cervical Foley bulb for induction of labor to decrease rate of cesarean deliveries in pregnancies complicated by gestational hypertension or preeclampsia ($\geq 24/0$ weeks' gestation)

The primary outcome will be rate of cesarean delivery. Secondary outcomes include interval time to delivery, acute use of anti-hypertensives and incidence of maternal/neonatal complications associated with use of IMN, to the point of discharge/transfer.

2.0 Specific Aims:

Specific aim 1: To determine if intravaginal administration of NOD isosorbide mononitrate (IMN) as an adjuvant to misoprostol/ intra-cervical Foley bulb for induction of labor decreases the rate of cesarean deliveries in pregnancies complicated by gestational hypertension or preeclampsia ($\geq 24/0$ weeks' gestation)

Specific aim 2: To determine if the use of intravaginal administration of NOD isosorbide mononitrate (IMN) as an adjuvant to misoprostol/ intra-cervical Foley bulb for induction of labor reduces the interval time to delivery.

Specific aim 3: To evaluate the safety of NOD isosorbide mononitrate (IMN) administered at the time of induction of labor in terms of frequency of intrapartum outcomes including placental abruption, need to treat with acute antihypertensive

medications, uterine hyperstimulation, maternal hypotension, atony, side effects (headache, nausea, vomiting, dizziness), and neonatal resuscitation.

3. Study Design

3.1 Primary Research Question:

Does intravaginal administration of NOD isosorbide mononitrate (IMN) as an adjuvant to misoprostol/ intra-cervical Foley bulb for induction of labor decrease the rate of cesarean deliveries in pregnancies complicated by gestational hypertension or preeclampsia?

Hypothesis 1: Compared to placebo, administration of intravaginal IMN as adjuvant to induction of labor decreases rate of cesarean deliveries in pregnancies complicated by gestational hypertension or preeclampsia.

3.2 Secondary Research Questions:

3.2.1 Does use of intravaginal NOD isosorbide mononitrate (IMN) as an adjuvant to misoprostol/ intra-cervical Foley bulb for induction of labor reduce the interval time to delivery?

Hypothesis 2: Compared to placebo, administration of intravaginal IMN at the time of induction of labor reduces the time interval from induction to vaginal delivery.

3.2.2 Is use of intravaginal IMN as an adjuvant induction agent in pregnancies complicated by preeclampsia associated with a favorable risk/benefit ratio?

Hypothesis 3: Administration of intravaginal IMN as an induction agent is safe and not associated with an increased risk of placental abruption, use of anti-hypertensives, maternal hypotension and uterine hyperstimulation, atony, meconium stained fluid compared to placebo, need for neonatal resuscitation.

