3.5.3 Randomization and Masking

After obtaining informed consent, women undergoing an induction of labor for preeclampsia will be randomized to either 30mg IMN given intravaginal with placement of misoprostol/foley bulb (as clinically indicated) or placebo in a 1:1 ratio. Randomization in each group will be by simple randomization, and will be computer generated. A confidential computer-generated simple randomization will be prepared and provided on an ongoing basis to a designated investigational pharmacist (all other study staff will be blinded). The investigational pharmacy will prepare identical appearing suppositories of IMN (30mg) or placebo according to the randomization sequence and deliver to a dedicated secure area in the labor and delivery area. A randomization log with study medication number, patient name and medical record number will be used to track the randomization process.

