- neonatal blood transfusion

- hypoxic–ischemic encephalopathy
- intraventricular hemorrhage grade 3 or 4
- necrotizing enterocolitis
- receipt of head cooling
- Other neonatal outcomes analyzed will be neonatal intensive care unit admission, neonatal intensive care unit admission greater than 48 hours, and neonatal length of stay (days).

5. Statistical Considerations

5.1 Sample size calculation:

Using data from our prior studies using the intended study population at The Ohio State Wexner Medical Center the incidence of gestational hypertension or preeclampsia is 10-15%.

Data abstracted from those enrolled in biorepository for gestational hypertension or preeclampsia over one year period and excluding those who were delivered for gestational hypertension or preeclampsia who had cesarean section for breech, prior cesarean section or uterine surgery, HELLP syndrome, eclampsia.

295 women underwent induction of labor for gestational hypertension or preeclampsia 48% (n=141) ended up with cesarean delivery after failed induction of labor or non-reassuring fetal well being.

Gestational Age Distribution for Gestational Hypertension or Preeclampsia Induction

Gestational Age in weeks	Number of women IOL for gHTN or PE	CS rate
24-28 wks	13	10 (77%)
28-30 wks	15	11 (73%)
30-32 wks	26	18 (69%)
32-34 wks	39	19 (49%)
34-36 wks	56	20 (34%)
36-37 wks	35	12 (34%)
37-38 wks	57	22 (38%)
38-39 wks	17	3 (18%)
39-40 wks	8	2 (25%)
40-41 wks	2	1 (50%)

Review of literature reveals is similar to OSU numbers, with the overall rate of cesarean delivery after induction of labor for gestational hypertension or preeclampsia ranges from 40% to 70%. Based on available data, we anticipate that the expected rate of the primary outcome in the women undergoing induction of labor for gestational hypertension or preeclampsia 45%. For this proposal, we will estimate a conservative relative reduction effect of 30-35%.

The table below provides the sample size calculations needed to achieve 80-90% power to detect 30-35% difference in the primary outcome between women receiving IMN or placebo at time of their induction of labor for preeclampsia, using a two-tailed alpha of 0.05.

Table 1. Total sample size required to detect a difference in primary outcome in women undergoing induction of labor and receiving IMN or placebo (alpha at 0.05, variable primary outcome rates, power, and effect sizes)

Relative reduction (%)	Power (%)	Primary Outcome Rate in Placebo group				

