		35%	40%	45%	50%	55%
30	90	784	644	540	462	380
	85	670	550	460	394	326
	80	586	480	404	346	284
33	90	656	540	430	368	306
	85	562	462	368	316	276
	80	490	404	322	276	242
35	90	586	482	406	330	290
	85	502	412	348	282	248
	80	438	362	304	248	216

Assuming the primary outcome to be 45 %, close to 1:1 enrollment and anticipating that no more than 2% of randomized women to be lost to follow up, a sample size of 400 women will achieve >85% power to detect a 33% relative reduction in primary outcome overall.

Given the study design and that randomization will occur once decision to proceed with induction occurs, there will be no concern for loss to follow up or missing outcome data on any women. Regarding concern for non-compliance, given study design we propose that it is unlikely that participant would not get their assigned treatment.

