5.3 Unblinding Criteria

This is a double-blind study—neither the patients nor the physician/health care providers are aware of the drug allocation during the duration of the study. In the event of a SAE thought to be related to the study drug, the patient will be treated as if she has received IMN. If medical care requires unblinding of the medication, the pharmacist will unblind the patient treatment assignment and notify the PI.

5.4 Feasibility: There are 5000 deliveries per year in at The Ohio State Wexner Medical Center and approximately 8% of women are diagnosed with gestational hypertension or preeclampsia and approximately 2/3 undergo induction of labor therefore approximately 264 women per year would be eligible for enrollment. Given the high-risk nature of this population it is reasonable to anticipate a consent and randomization rate which is higher than that which is accounted for above. With only 50% consent rate, 132 women may be randomized annually. Our conservative estimate suggests that this study can be completed in approximately 3 years.

5.5 Data analysis: Analysis will be by intent-to-treat. Preliminary analyses will be conducted to test homogeneity of treatment groups for demographic data (gravidity, gestational age at randomization, race/ethnicity, BMI, number of prior cesarean) using the two-sample *t* test for continuous measurements and the Pearson chi-square test for categorical measurements. Primary and secondary outcomes will be analyzed between the two groups using univariable and multivariable analyses as needed.

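### Hypothesis 3 sets out to conclude that IMN causes no increase in harm, but the plan has no criterion that could support this, and 400 women cannot support it for uncommon harms such as abruption

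*Combined protocol and SAP*

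**What the plan says.** Section 3.2.2, Hypothesis 3, is worded as a conclusion to be supported: "Administration of intravaginal IMN as an induction agent is safe and not associated with an increased risk of placental abruption". It goes on to name antihypertensive use, maternal hypotension, uterine hyperstimulation, atony, meconium-stained fluid and neonatal resuscitation, which makes seven harms in all.

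Specific Aim 3 in section 2.0 is more neutral. It evaluates safety of IMN "administered at the time of induction of labor in terms of frequency of intrapartum outcomes including placental abruption" and other events.

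The only analysis text for these outcomes is in section 5.5: "Primary and secondary outcomes will be analyzed between the two groups using univariable and multivariable analyses as needed". No test, margin, interval or threshold is named for any harm.

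The sample size in section 5.1 rests on cesarean delivery alone: "Assuming the primary outcome to be 45 %, close to 1:1 enrollment" and "a sample size of 400 women will achieve >85% power to detect a 33% relative reduction in primary outcome overall", "using a two-tailed alpha of 0.05". Section 5.2 gives maternal safety outcomes emphasis in the interim reports but sets no threshold for them.

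**The concern.** Hypotheses 1 and 2 assert a difference, so an ordinary significance test can support them. Hypothesis 3 asserts that there is no increase, and an ordinary test cannot support that: a non-significant result may reflect no effect or too few events. A no-increase claim needs a margin, or an interval whose upper limit is low enough to matter, and the plan has neither.

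At stake is what the trial may say about safety. Section 3.2.2 asks whether the risk/benefit ratio is favorable, so the answer to Hypothesis 3 feeds the overall message. The drug is a vasodilator given to hypertensive women in labor. If the absence of a significant difference in a rare event were reported as absence of risk, the statement would go beyond the data.

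**Working it through.** **Inputs from the documents.** 400 women in total (5.1), allocated 1:1 (3.5.3), so about 200 per arm. Two-sided alpha is 0.05, which 5.1 states for the primary outcome only; applying it to harms is my assumption. Loss is at most 2% (5.1), which would leave about 196 per arm.

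**Assumed input.** The documents give no placebo rate for abruption. I take 0.5% to 5%, doubled under IMN, and use 10% to represent a common harm.

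**Step 1: the plan's own power.** With p1 = 0.45 and p2 = 0.45 × 0.67 = 0.3015, the mean is 0.37575. Power = Φ{[|p1 − p2|√n − 1.96√(2p̄(1 − p̄))] / √(p1(1 − p1) + p2(1 − p2))}.
- n = 200: (0.1485 × 14.142 − 1.96 × 0.6849) / 0.6768 = 1.12, so power is 86.8%.
- n = 196: power is 86.2%.

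The stated figure of more than 85% is reproduced for cesarean delivery.

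**Step 2: power to detect a doubling of a harm.** Exact power is the sum, over all event counts i (placebo) and j (IMN), of Bin(i; 200, p) × Bin(j; 200, 2p), counting the pairs where j > i and the two-sided test gives p < 0.05.

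| Assumed placebo rate | IMN rate | Chi-square | Fisher |
|---|---|---|---|
| 0.5% | 1% | 5% | 1% |
| 1% | 2% | 11% | 4% |
| 2% | 4% | 21% | 13% |
| 3% | 6% | 30% | 22% |
| 5% | 10% | 47% | 41% |
| 10% | 20% | 81% | 77% |

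As a hand check at 2% versus 4%, the formula in step 1 gives (0.02 × 14.142 − 1.96 × 0.2412) / 0.2408 = −0.79, that is 21.5%. With 196 per arm no entry changes by more than about one percentage point.

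At 1% to 3%, a true doubling would therefore go undetected in about 89%, 79% and 70% of trials by chi-square (100% minus power), and in 96%, 87% and 78% by Fisher. A miss is more likely than not throughout the 0.5% to 5% range.

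**Step 3: what the counts would look like.** At 1% versus 2% the expected counts are 200 × 0.01 = 2 and 200 × 0.02 = 4; Fisher's p for 2 versus 4 is 0.69. With 2 placebo events, Fisher needs 10 IMN events to fall below 0.05, a fivefold excess.

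**Step 4: what equal counts would exclude.** Suppose 2/200 in each arm. The Wilson limits for one arm are 0.27% and 3.57%. Newcombe's half-width is √[(1.00 − 0.27)² + (3.57 − 1.00)²] = 2.7 percentage points, so the interval for the risk difference is −2.7 to +2.7 points. The score interval for the risk ratio is about 0.18 to 5.6; the log method gives 0.14 to 7.0. A doubling from 1% adds 1 point and lies well inside all of these.

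**The case against.** The strongest objection is that no passage says p>0.05 means safe. A reader might infer that the trial would, as written, declare IMN safe after a non-significant test. The documents do not go that far: section 5.5 names no test and no decision rule, the alpha in 5.1 belongs to the primary outcome, and a univariable analysis could well report intervals. This objection stands. What can be shown is that Hypothesis 3 states a conclusion and the plan gives no criterion for reaching it.

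Second, Aim 3 is already worded as the frequency of events, close to estimation. This also stands: the problem lies in Hypothesis 3, and the two passages differ in how much they claim.

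Third, some of the harms in Hypothesis 3 may be common. At an assumed placebo rate of 10%, power for a doubling is 81% by chi-square and 77% by Fisher. The argument is therefore about uncommon harms and weakens for common ones. The documents give no rates from which to say which of the other listed harms fall into which group.

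Fourth, low power for rare harms is usual in a trial sized for efficacy. That is true, and it is no reason to enroll more women. It is a reason not to prespecify a claim of safety that the design cannot support.

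**Conclusion.** The point holds in limited form. Hypothesis 3 targets a no-increase conclusion, and the plan contains no margin, interval or other criterion that could support one. That a non-significant comparison would be taken as the support is an inference from the wording of the hypothesis and from section 5.5, not a stated rule.

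For uncommon harms, 400 women cannot carry the claim. Under assumed placebo rates of 1% to 3%, power to detect a doubling is about 11% to 30% by chi-square and 4% to 22% by Fisher. These figures rest on the assumed rates, on about 200 women per arm and on a two-sided 0.05 level. Near 5% a miss is only slightly more likely than not by chi-square, and at 10% or above the concern is much smaller.

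It would be wrong to read this as evidence that IMN is harmful, or as a fault in the primary analysis, whose stated power is reproduced. What should change is what the trial may conclude about safety.

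**What to change.** 1. In 3.2.2, reword Hypothesis 3 as estimation, in line with Aim 3: the trial will estimate the difference in the risk of each listed harm between IMN and placebo.
2. In 5.5, prespecify for each listed harm the event counts, the risk difference and the risk ratio, with 95% confidence intervals by a named method suited to small counts (for example Newcombe for the difference and score for the ratio).
3. State in 5.5 that p>0.05 will not be read as evidence of safety.
4. Word the safety conclusion as the largest excess risk that the interval excludes. With 2 events in each arm, for example, this would be an excess above about 2.7 percentage points.
5. Add atony, meconium-stained fluid and neonatal resuscitation to the outcome list in 4.2. Hypothesis 3 names them but 4.2 does not.

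No non-inferiority margin or larger sample is needed, and the primary analysis does not change. The cost is some wording, a few intervals and, for item 5, confirmation that the three outcomes are being abstracted. The downside is that the trial gives up an unqualified claim that IMN is safe.

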3.3 Design Summary

[figure not shown]
We are proposing a double blinded, placebo controlled, randomized clinical trial of patients undergoing induction of labor for gestational hypertension or preeclampsia. Once the decision to induce will be taken, mothers will be randomized to receive either intravaginal IMN (30mg) or identical appearing placebo placed every 4hrs in the posterior vaginal fornix X 3 doses. IMN or placebo will be discontinued when active labor occurs or when the physician decides to proceed with augmentation with oxytocin or AROM. Participants will be induced using our routine induction agents, Misoprostol (25 mcg every 4 hrs for maximum of 6 doses) and an intra-cervical foley bulb will be inserted with 2nd dose of IMN or placebo. See figure 1, for further details. Regarding management of labor, physician decides when to proceed with augmentation with oxytocin or AROM.

An intra-cervical foley bulb will be placed with 2nd dose of IMN (or placebo). If unable to be placed, a higher level provider must attempt placement, if still unable to be placed the patient will be examined every 4 hours and Foley bulb placement was reattempted if Bishop's score is still 6 or less. When the Foley bulb had fallen out, further management of labor will be at the discretion of the labor team and included expectant management, amniotomy, or IV oxytocin. If indicated,

IV oxytocin will be started per standard protocol after 4 hours from the last misoprostol dose. The rest of the obstetrical care will be similar in all arms and guided by clinical guidelines.

Figure 1. Detailed algorithm of enrollment

Isosorbide mononitrate or Placebo Combined with Misoprostol and Foley Protocol

- IMN should be administered intravaginal every 4 hours for maximum of 3 doses
- Misoprostol should be administered intravaginal every 4 hours for maximum of 6 doses, if < 4 contractions in 10 minutes and bishop score <6
- If cervical Foley bulb cannot be placed at initial exam, a second higher level provider must attempt. If still unable to place, repeat exam in 1-2 hours from misoprostol placement to reattempt Foley placement.
- In order to call it a failed placement attempt, an attempt must be made with patient placed in stirrups and under direct visualization.
- Remove Foley if still in place after 12 hours from placement. Can continue with misoprostol use after Foley is removed as long as it meets criteria noted above.
- Oxytocin can be initiated 4 hours after placement of last misoprostol, regardless of whether cervical Foley still in situ

